1.5. Compliance

This study will be conducted in compliance with this protocol, Good Clinical Practice (GCP), and all applicable regulatory requirements.

2. OBJECTIVES

The primary objective of this study is:

- To evaluate the effect of filgotinib on testicular function as defined by the proportion of subjects with a $\geq 50\%$ decrease from baseline in sperm concentration at Week 13

The secondary objectives of this study include:

- To evaluate the effect of filgotinib on testicular function as defined by the proportion of subjects with a $\geq 50\%$ decrease from baseline in sperm concentration at Week 26
- To evaluate the effect of filgotinib on sperm total motility at Weeks 13 and 26
- To evaluate the effect of filgotinib on total sperm count at Weeks 13 and 26
- To evaluate the effect of filgotinib on the change from baseline in sperm concentration at Weeks 13 and 26
- To evaluate the effect of filgotinib on ejaculate volume at Weeks 13 and 26
- To evaluate the effect of filgotinib on sperm morphology at Weeks 13 and 26

The exploratory objectives of this study include:

- To evaluate the reversibility of observed effects of filgotinib on testicular function in subjects who experience a $\geq 50\%$ decrease in sperm concentration, and/or motility and/or morphology
- To evaluate the effect of filgotinib on sex hormones, including luteinizing hormone (LH), follicle stimulating hormone (FSH), inhibin B, and total testosterone at Weeks 13 and 26
- To evaluate the safety and tolerability of filgotinib
- To characterize the plasma pharmacokinetics (PK) of filgotinib and its metabolite (GS-829845, formerly CCI)

3. STUDY DESIGN

This is a randomized, double-blind, placebo-controlled Phase 2 study in adult males with moderately to severely active UC, or moderately to severely active CD, who may be on protocol-specified concomitant therapy.

Up to 250 males between the age of 21 and 65 years (inclusive) at the time of consent will be randomized to receive up to 26 weeks of filgotinib 200 mg or placebo-to-match (PTM) filgotinib 200 mg once daily, to ensure approximately 200 subjects are evaluable.

[figure not shown]
Randomization will be stratified according to the type of IBD (ie, UC versus CD), by concurrent use of MTX (yes or no), and by sperm concentration measured at Screening (“Baseline”) according to the following strata:

- 15 to 25 million/mL
- > 25 to 50 million/mL
- > 50 million/mL

Male subjects with moderately to severely active IBD who provide written informed consent will be screened to determine eligibility as per the inclusion and exclusion criteria (see Section 4.2 and 4.3, respectively). The Screening period will be up to 45 days, and may be extended in consultation with the medical monitor.

The assessments to be performed at each visit are detailed in the study procedures table (Appendix 2). A schematic of the study design is provided below.

Figure 3-1. Study Schema

*A mean of 2 semen samples at Screening must meet the following minimum criteria: semen volume ≥ 1.5 mL, total sperm/ejaculate ≥ 39 million, sperm concentration ≥ 15 million/mL, sperm total motility $\geq 40\%$, and normal sperm morphology $\geq 30\%$
 †All subjects with $\geq 50\%$ decrease in sperm concentration and/or sperm motility and/or sperm morphology as compared to baseline will enter a Monitoring Phase (discontinue study drug and evaluate for Reversibility)
 ‡ At/after Week 13, protocol design allows a switch to open-label filgotinib for Non-responders or those with Disease Worsening; semen analysis is required to confirm that no pre-specified decrease threshold is met, prior to administration of open-label filgotinib

[figure not shown]
There are 5 distinct parts to the study which subjects may enter depending upon the individual response of the underlying IBD to assigned treatment and/or observed changes in semen parameters. The 5 parts which are described in the following sections comprise of the following:

- 1) Part A (Day 1 through Week 13 Study Visit)
- 2) Part B (After Week 13 through Week 26 Study Visit)
- 3) Open-Label Filgotinib Phase
- 4) Monitoring Phase
- 5) Long Term Extension

The study parts are described in the following sections.

Subjects will visit the clinical study center to be evaluated for clinical and laboratory assessments at Screening, Day 1, Week 2, Week 4, Week 8, and Week 13, including semen sample collection during Week 13 visits. Subjects who continue on blinded treatment after the first 13 weeks of treatment will return for Week 20 and Week 26 assessments, including semen sample collection during Week 26 visits.

[figure not shown]
Figure 3-2. Part A (Day 1 through Week 13 Study Visit)

In Part A, all subjects will receive blinded study drug for the first 13 weeks, starting from the Day 1/Randomization Study Visit. At the Week 13 Study Visit, IBD response status (ie, Non-responder vs Responder, see Definition of Terms) will be determined based on the partial Mayo Clinic Score (partial MCS) for subjects with UC, or Crohn’s Disease Activity Index (CDAI) for subjects with CD. In addition, sperm parameters (see Section 6.13 Semen Collection Procedure) will be evaluated to determine whether any of the pre-specified decrease thresholds (see Definition of Terms) have been met.

- Subjects who are Responders whose sperm parameters do not meet a pre-specified decrease threshold will continue blinded study drug in Part B.
- Subjects who are Non-responders whose sperm parameters do not meet a pre-specified decrease threshold will discontinue blinded study drug and commence open-label (OL) filgotinib.
- Subjects whose sperm parameters meet a pre-specified decrease threshold, regardless of IBD response status, will discontinue blinded study drug and enter the Monitoring Phase.

[figure not shown]
Figure 3-3. Part B (After Week 13 through Week 26 Study Visit)

In Part B, all subjects will continue on blinded study drug for up to an additional 13 weeks. Subjects may experience Disease Worsening (see Definition of Terms) of their underlying IBD at any time during blinded study drug treatment (after Week 13 through Week 26). If Disease Worsening is confirmed, sperm parameters will be evaluated to determine whether a pre-specified decrease threshold has been met prior to a study drug change (changing from blinded study drug to OL filgotinib). Based upon the sperm parameters at this time point, subjects may follow one of the following pathways:

- All subjects whose sperm parameters meet a pre-specified decrease threshold, regardless of IBD response status, will discontinue blinded study drug, complete a safety follow-up visit 30 days after last study drug dose, and enter the Monitoring Phase.
- Subjects who experience Disease Worsening after Week 13 and prior to Week 26, and whose sperm parameters do not meet a pre-specified decrease threshold will discontinue blinded study drug and commence OL filgotinib.
- Subjects who do not experience Disease Worsening, are Responders at Week 26, and whose sperm parameters do not meet a pre-specified decrease threshold, will continue blinded study drug as part of the Long Term Extension (LTE).
- Subjects who do not experience Disease Worsening, but are Non-responders at Week 26, and whose sperm parameters do not meet a pre-specified decrease threshold, will discontinue blinded study drug and complete a safety follow-up visit 30 days after last study drug dose.

Figure 3-4. Open-Label Filgotinib Phase (Open-Label Day 1 through Open-Label Week 13 Study Visit)

As above, after the first 13 weeks of exposure to blinded study drug those subjects who are deemed Non-responders at Week 13 or those who meet Disease Worsening criteria after Week 13 and prior to Week 26 may qualify for entry into the OL Filgotinib Phase and return for study assessments at OL Day 1, OL Week 2, OL Week 4, OL Week 8, and OL Week 13. After exposure to 13 weeks of OL filgotinib in the OL Filgotinib Phase, the subject's IBD response status will again be determined using the partial MCS (in the case of UC) or CDAI score (in the case of CD), and sperm parameters will be evaluated to determine whether a pre-specified decrease threshold has been met:

[figure not shown]
- All subjects whose sperm parameters meet a pre-specified decrease threshold, regardless of Responder status, will discontinue OL filgotinib, complete a safety follow-up visit 30 days after last study drug dose, and enter the Monitoring Phase.
- Subjects who experience Disease Worsening during OL filgotinib treatment and whose sperm parameters do not meet a pre-specified decrease threshold will discontinue OL filgotinib, complete Early Termination (ET) and a safety follow-up visit 30 days after last study drug dose.
- Subjects who do not experience Disease Worsening, and are Responders at OL Week 13 after exposure to 13 weeks of OL filgotinib, and whose sperm parameters do not meet a pre-specified decrease threshold, will continue receiving OL filgotinib as part of the LTE.
- Subjects who do not experience Disease Worsening, but are Non-responders after exposure to 13 weeks of OL filgotinib, and whose sperm parameters do not meet a pre-specified decrease threshold, will discontinue OL filgotinib and complete a safety follow-up visit 30 days after last study drug dose.

Figure 3-5. Monitoring Phase (up to 52 weeks)

All subjects who enter the Monitoring Phase will undergo semen evaluations every 13 weeks from the day of study drug discontinuation, for up to 52 weeks or until Reversibility is met, whichever is achieved first. Subjects will be offered locally approved SOC therapy during the Monitoring Phase.

Figure 3-6. Long Term Extension (up to 195 weeks)

Subjects continuing on to the LTE will undergo scheduled visits for safety assessments every 13 weeks up to 195 weeks, and semen monitoring will be collected every 13 weeks until the Week 13 primary study results are analyzed. All subjects who enter the LTE will receive either OL filgotinib or blinded study drug based on the individual’s response criteria described above. If a subject experiences Disease Worsening during the LTE, the treatment (either OL filgotinib or blinded study drug) will be discontinued, and the subject will receive locally approved SOC therapy as determined by the primary investigator. Subject will complete an ET visit, followed by a safety follow-up visit 30 days after last study drug dose.

Sparse plasma PK Sample Collection:

In Parts A and B, sparse plasma PK samples will be collected at least 30 minutes post dose at the Week 2 visit, anytime at the Week 4 visit, and predose during visits at Weeks 13 and 26. In the OL Filgotinib Phase, sparse plasma PK samples will be collected at least 30 minutes post dose at the OL Week 2 visit, anytime at the OL Week 4 visit, and predose during visits at OL Week 13.

Semen Collection and Analysis:

At each of the following time points, subjects will provide 2 separate semen samples collected within a 14-day period. Each semen sample must be collected with an ejaculation free period of ≥ 48 hours and ≤ 7 days (Section 6.13).

- Screening (Baseline)
- After Part A (Week 13 Study Visit)
- After Part B (Week 26 Study Visit)

OR

For Subjects who experience confirmed Disease Worsening between Weeks 13-26 in Part B, prior to beginning OL Filgotinib Phase and at the OL Week 13 Study Visit

- Every 13 weeks during the Monitoring Phase (if applicable)
- Every 13 weeks during the LTE

In select instances where the semen sample with questioned value(s) is found to be non-assessable or invalid (eg, collection without adherence to ejaculation-free periods; intercurrent illness or dehydration at time of collection; incomplete capture of semen sample; and/or sample processing or semen analysis that deviates from standardized procedure), a third semen sample, when indicated, must be collected within 14 days of the prior sample, with an ejaculation free period of ≥ 48 hours and ≤ 7 days. All decisions of retesting any semen/sperm parameter (ie, obtaining a third semen sample at any of the above time points) must be confirmed by the Sponsor Medical Monitor or designee before the retest.

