Unblinded interim analyses of the clinical trial data will be performed by the Sponsor for regulatory submissions when 200 subjects (eg, pooled data from GS-US-418-4279 and GLPG0634-CL-227), and/or when some defined subset(s) of subjects, have completed the Week 13 and Week 26 (or OL Week 13) assessments (first unblinded interim analysis [IA1]), and when complete reversibility data for all subjects who entered the Monitoring Phase at these time points is available (IA2; see Definition of Terms). A Data Integrity and Communication Plan for the interim analysis will be developed prior to unblinding. The analyses will

be conducted primarily to evaluate the testicular safety and further details will be described in the statistical analysis plan (SAP).

For ongoing subjects, the study teams and study staff at the sites and all other staff directly involved in the conduct of the study will remain blinded to the treatment assignments until the final analysis when the database has been locked. Publication of the IA2 data is planned by the Sponsor. This publication will contain group level data for the entire study population, but will unblind the study teams and staff directly involved in the conduct of the study to the individual baseline treatment assignment of subjects who completed the study before IA2.

This study will be conducted in accordance with the guidelines of Good Clinical Practice (GCP) including archiving of essential documents.

DEFINITION OF TERMS

Disease Worsening	
For subjects with UC, Disease Worsening is defined by a partial MCS after Week 13 consisting of:
 
an increase of ≥ 3 points to at least 5 points from the Week 13 value on 2 consecutive visits, OR
 
an increase to 9 points from the Week 13 value on 2 consecutive visits, if the Week 13 value was > 6 points
 
For subjects with CD, Disease Worsening is defined by a total CDAI score after Week 13 consisting of:
 
a score ≥ 220 on 2 consecutive visits, AND
 
an increase of ≥ 100 points from the Week 13 value on 2 consecutive visits
 
Disease Worsening is confirmed at the time of the second consecutive visit.

Mayo Clinic Score (MCS)	
Composite score of UC activity consisting of sub-scores from endoscopy, rectal bleeding, stool frequency, and PGA. Subject recall for the last 24 hours will be used for the patient reported components of the complete MCS.

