Pre-specified decrease threshold	A $\geq 50\%$ decrease in sperm concentration, and/or motility, and/or morphology in comparison to Baseline. The mean of values for each of the sperm parameters (measured from 2 separate semen samples) will be used in all analyses. Samples will be collected within a 14-day period, with an ejaculation-free period of ≥ 48 hours and ≤ 7 days.
Reversibility	Reversibility is met when all sperm parameter(s) qualifying the subject to enter into the Monitoring Phase return(s) to greater than 50% of Baseline (ie, to greater than $[0.50 \times \text{mean of 2 sperm collections collected at the Screening visit (eg, Baseline)}]$).
Week 13	The Week 13 Study Visit occurs once a subject completes the first 13 weeks of blinded study drug, and is inclusive of all study assessments performed at the clinic visit and the semen sample collection visits associated with this time point.
Week 26	The Week 26 Study Visit occurs once a subject completes the second 13 weeks of blinded study, and is inclusive of all study assessments performed at the clinic visit and the semen sample collection visits associated with this time point.
OL Week 13	The OL Week 13 Study Visit occurs once a subject completes the first 13 weeks of OL filgotinib, and is inclusive of all study assessments performed at the clinic visit and the semen sample collection visits associated with this time point.

First unblinded interim analysis (IA1)	Unblinded Week 26 analysis to be performed after at least 200 evaluable subjects pooled across studies GS-US-418-4279 (GLPG0634-CL-228) and GLPG0634-CL-227 complete Week 13 and evaluable subjects from Study GS-US-418-4279 complete Week 26 (or OL Week 13) or permanently discontinue from study drug. Referred to as 'Week 26 Analysis' in the SAP.
Second unblinded interim analysis (IA2)	Unblinded Week 26 analysis to be performed after all subjects reach Week 26 and all subjects with a $\geq 50\%$ decrease in sperm concentration, and/or motility, and/or morphology up to Week 26 (or OL Week 13) enter the Monitoring Phase and either meet reversibility criteria or are followed off-treatment for 52 weeks, whichever occurs first. Referred to as 'Week 26 and Reversibility Analysis for Pre-specified Sperm Decreases Up to Week 26' in the SAP.

GLOSSARY OF ABBREVIATIONS AND DEFINITION OF TERMS

5-ASA	5-aminosalicylate
6-MP	6-mercaptopurine
Ab	antibody
AE	adverse event
ALT	alanine aminotransferase
ANCOVA	analysis of covariance

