Overall clinical findings and laboratory changes reported with filgotinib are consistent with JAK 1 inhibition. Based on Phase 2 data the expected benefit of using filgotinib as proposed in this study is considered to outweigh any associated risks. In addition, the subject population in the present study will consent to a risk of potentially permanent infertility, thus individual male subjects in conjunction with the treating physician may evaluate the benefit-risk profile of filgotinib. A lack of response contingency from Week 13 onward in the current study, targeting Non-responders at Week 13 and any subject who experiences Disease Worsening thereafter, will enable early access to active drug or standard of care treatment when clinically indicated. This rescue approach, the provision of best supportive care, and the limited study duration, makes the use of placebo ethically acceptable for the specified duration.

An external multidisciplinary DMC, including an expert in male fertility, will be appointed to monitor the study.

The DMC has monitored the study until the date of protocol amendment 6, including the data for the second unblinded interim analysis (IA2). As of amendment 6, the DMC will be decommissioned. Details on the DMC's role have been described in a specific charter. The DMC's role will be transferred to the internal Sponsor Safety Management Team (SSMT). The SSMT is not involved in the conduct of the study and will evaluate safety data throughout the remainder of the study as part of continuous safety oversight across the filgotinib program.

Taking all of these considerations into account with respect to the filgotinib program, the early signals for efficacy demonstrated in a Phase 2 clinical trial in CD, as well as the beneficial findings in nonclinical models of disease and the overall safety, tolerability, and PK characteristics of filgotinib elucidated to date, there is a favorable benefit-risk profile for this agent in continued development as a treatment for UC and CD. The overall benefit-risk balance of this study is considered favorable.

For additional information about the risks of filgotinib, reference the latest version of the filgotinib IB.

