3.4. Disease Worsening Criteria

Subjects meeting the following Disease Worsening criteria, evaluated after Week 13 through Week 26, must be discontinued from blinded treatment. These subjects will be offered the option to commence OL filgotinib 200 mg once daily, as long as they have not experienced a decrease of $\geq 50\%$ from baseline in sperm concentration, and/or motility, and/or morphology.

Upon confirmation of Disease Worsening and before switching to the OL Filgotinib Phase, 2 semen samples will be collected. Disease Worsening is confirmed at the time of the second consecutive visit. If the second Disease Worsening visit occurs during the 14-day semen

collection window for the Week 13 or Week 26 Study Visit, the routine Week 13 or Week 26 semen collection will suffice.

Disease Worsening assessments will be driven by the patient history, physical and laboratory examinations and are based on the following criteria:

For subjects with UC, Disease Worsening is defined by a partial MCS after Week 13 consisting of:

- An increase of ≥ 3 points to at least 5 points from the Week 13 value on 2 consecutive visits, OR
- An increase to 9 points from the Week 13 value on 2 consecutive visits, if the Week 13 value was > 6 points

For subjects with CD, Disease Worsening is defined by a total CDAI score after Week 13 consisting of:

- A score ≥ 220 on 2 consecutive visits, AND
- An increase of ≥ 100 points from the Week 13 value on 2 consecutive visits

For all subjects, Disease Worsening is further defined by:

- Disease Worsening to the extent that the subject requires medications prohibited by the study (at investigator's discretion, with discussion with the medical monitor or designee if feasible); these subjects do not qualify to receive OL filgotinib 200 mg once daily.

Disease Worsening visits may include Unscheduled Visits (eg, a Study Visit followed by an Unscheduled Visit, or 2 sequential Unscheduled Visits after Week 13).

In the LTE, subjects who meet Disease Worsening criteria (per above criteria), or have Disease Worsening per investigator judgment, should be discontinued from study drug. These subjects should complete an ET visit (which includes semen collection), followed by a routine safety follow-up visit 30 days after the last dose of study drug.

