7.1.1. Calculations of MCS and pMCS with the Subscores

The MCS is an instrument designed to measure disease activity in ulcerative colitis (Table 7-1). The MCS system is a composite index of 4 disease activity variables. Each variable is scored individually on an integer scale of 0 to 3, inclusive, with higher scores indicating greater disease activity. The individual components of the MCS include stool frequency (SF), rectal bleeding (RB), endoscopic subscore, and the physician's global assessment (PGA). Individual components of the MCS are described in Table 7-1 and MCS is calculated as the sum of the 4 subscores, ranging from 0 to 12. A pMCS is calculated as the sum of the 3 subscores excluding the endoscopic subscore; pMCS ranges from 0 to 9.

Table 7-1. Mayo Clinic Score

Variables	Score			
	0	1	2	3
Endoscopic Findings	Normal or inactive	Mild disease	Moderate disease	Severe disease
Rectal Bleeding	None	Streaks of blood in stool less than half the time	Obvious blood in stool half or more than half of the time	Blood alone passes
Stool Frequency (per subject recall)	Normal number of daily stools for patient	1-2 stools per day more than normal	3-4 stools per day more than normal	≥ 5 stools per day more than normal
Physician Global Assessment	None	Mild disease	Moderate disease	Severe disease

A Responder for UC is defined as a subject who has a reduction of ≥ 2 in pMCS compared to baseline at the specified assessment timepoint. A Non-responder will be defined as a subject who does not fulfill the definition of responder at the specified assessment timepoint.

Disease Worsening for UC is defined by a pMCS after Week 13 consisting of:

- an increase of ≥ 3 points to at least 5 points from the Week 13 value on 2 consecutive visits, or
- an increase to 9 points from the Week 13 value on 2 consecutive visits, if the Week 13 value was > 6 points

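### The open-label stop for Disease Worsening has no open-label reference score in the visible text; read literally, a UC man who entered by worsening still meets it until his pMCS falls 1 to 5 points

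*Protocol*

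**What the plan says.** The Open-Label Filgotinib Phase pathways in protocol Section 3 state: "Subjects who experience Disease Worsening during OL filgotinib treatment and whose sperm parameters do not meet a pre-specified decrease threshold will discontinue OL filgotinib". The synopsis has the same rule without the words that place the event in open-label treatment.

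The Definition of Terms fixes the term by score: "For subjects with UC, Disease Worsening is defined by a partial MCS after Week 13 consisting of", followed by two limbs. The first asks for a rise of 3 or more points "to at least 5 points from the Week 13 value on 2 consecutive visits". The second asks for a score of 9 when the Week 13 score was above 6. Section 3.4 repeats both and adds that "Disease Worsening is confirmed at the time of the second consecutive visit". SAP Section 7.1.1 uses the same anchor: "Disease Worsening for UC is defined by a pMCS after Week 13 consisting of". The Crohn's disease (CD) limb is also measured from Week 13.

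Week 13 is the blinded visit: "The Week 13 Study Visit occurs once a subject completes the first 13 weeks of blinded study drug". OL Week 13 is defined as a separate term.

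Section 3.4 says that men meeting the criteria, "evaluated after Week 13 through Week 26, must be discontinued from blinded treatment". It extends the criteria explicitly only to the Long Term Extension (LTE), where it adds investigator judgment. The SAP's Open-label Baseline (Section 3.7.1) serves safety assessments and is not linked to Disease Worsening.

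**The concern.** The same criterion admits a man to open label and removes him from it. If the reference stays at his blinded Week 13 score, a man who flared in Part B arrives already at or above his exit threshold. He need not get worse to be stopped; he only has to improve too slowly.

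An example: baseline pMCS 6, Week 13 score 2, flare to 8. On open label he scores 7 at OL Week 2 and 6 at OL Week 4. Both scores are at least 5 and at least 3 above his Week 13 value, so worsening is confirmed while he improves. At that pace he would score 4 at OL Week 13, which is a 2-point reduction from baseline and makes him a Responder.

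What is at stake is access to rescue, on which Section 1.4 relies: "This rescue approach, the provision of best supportive care, and the limited study duration, makes the use of placebo ethically acceptable". Two sites could also reach opposite decisions on the same scores, each with support in the text.

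**Working it through.** The plan states no figure for this rule, so there is none to reproduce. The check enumerates every integer pMCS.

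**Inputs.** pMCS runs from 0 to 9 (Appendix 3). Part B holds Week 13 Responders only (Section 6.5), and a UC Responder has a reduction of at least 2 from baseline (Definition of Terms), so the Week 13 score w is at most 7. Visits with pMCS after OL Day 1 are OL Weeks 2, 4, 8 and 13 (Appendix 2).

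**Rule.** A score s counts as Disease Worsening if (s − w ≥ 3 and s ≥ 5), or if (w > 6, s = 9 and s > w).

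| Week 13 score w | Possible entry scores | Lowest score still meeting the rule | Fall needed to leave it |
|---|---|---|---|
| 0, 1 or 2 | 5–9 | 5 | 1–5 |
| 3 | 6–9 | 6 | 1–4 |
| 4 | 7–9 | 7 | 1–3 |
| 5 | 8–9 | 8 | 1–2 |
| 6 or 7 | 9 | 9 | 1 |

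Pairs: 3×5 + 4 + 3 + 2 + 2×1 = 26. Pairs still meeting the rule after a fall of 0, 1, 2, 3, 4 or 5 points: 26, 18, 12, 7, 3, 0.

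**Two consecutive visits, assumed fall of 1 point per visit.**
- OL Weeks 2 and 4 (falls of 1 and 2): the rule must still hold after 2 points, so 12 of 26. These are entry 7 with w 0–2 (3 pairs), entry 8 with w 0–3 (4) and entry 9 with w 0–4 (5).
- OL Weeks 8 and 13 (falls of 3 and 4): 3 of 26, namely entry 9 with w 0–2.

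**Assumed fall of 2 points per visit.** OL Weeks 2 and 4 (falls of 2 and 4): 3 of 26. OL Weeks 8 and 13 (falls of 6 and 8): 0.

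**Would the man have responded?** This needs baseline b. Assume b = 3 to 9, from an eligibility Mayo score of at least 6 with an endoscopic subscore of at most 3. With w ≤ b − 2 the number of baselines is 7, 7, 6, 5, 4, 3, 2, 1 for w = 0 to 7. States: 5×7 + 5×7 + 5×6 + 4×5 + 3×4 + 2×3 + 2 + 1 = 141.
- 1 point per visit, OL Weeks 2 and 4: stopped in 20 (entry 7) + 25 (entry 8) + 29 (entry 9) = 74 states. OL Week 13 scores would be 3, 4 and 5, and response needs b of at least 5, 6 and 7. Responders lost: 3×5 + 4×4 + 5×3 = 46 of 141.
- 1 point per visit, OL Weeks 8 and 13: the OL Week 13 score is 5 and response needs b of 7–9, so 3×3 = 9 of 141.

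**OL Day 1 as reference.** A man entering at 5 would meet the rule only at 8 or 9, and one entering at 6, 7 or 8 only at 9. No stable or improving man meets it. A man entering at 9 cannot meet it by score (8 of 26 pairs).

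**The case against.** The strongest reply is that the literal reading is not the only one.

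- The pathway speaks of experiencing Disease Worsening during open-label treatment, which can mean a new event and not the flare that opened the phase.
- The Section 3 pathways are introduced as an assessment after 13 weeks of open-label drug, and each needs a sperm result. Semen in this phase is scheduled at OL Week 13, apart from early termination. Judged then, the counts are the smaller ones: 3 of 26 and 9 of 141.
- Section 3.4 ties its score criteria to blinded treatment. It also has a limb that needs no reference score (need for prohibited medication). Section 3.3.2 asks for medical monitor consultation before discontinuation, and encourages men offered open-label drug to continue if medically appropriate.
- The trajectories are constructed and the states unweighted. In 52 of the 74 stopped states the entry score exceeds the randomization baseline.

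Most of this stands and limits the size. It does not close the gap: none of these provisions supplies another reference score, and the Definition of Terms keeps the Week 13 anchor for the defined term. The early-termination visit does not settle the timing, because Section 6.8 also asks it of OL Week 13 Responders who decline the LTE.

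A reader might infer that the protocol certainly withdraws improving men at OL Week 4, or that no open-label reference exists anywhere. The documents support neither: the timing is unsettled, and a reference shown only in Figure 3-4 or Appendix 11 cannot be excluded.

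**Conclusion.** The concern holds as an ambiguity with a harmful literal reading. In the visible text, open-label drug is stopped on a defined term whose only score anchor is the blinded Week 13 value. A UC man who entered by worsening therefore meets the exit score until his pMCS falls 1 to 5 points.

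The size rests on when worsening is judged and how fast scores fall, neither of which the documents settle. At 1 point per visit it is 12 of 26 pairs (46 of 141 states losing a later response) on the early reading and 3 of 26 (9 of 141) on the late one. At 2 points per visit it is 3 and 0 of 26. Section 3.4 lets unscheduled visits count, so confirmation could come earlier than these schedules assume.

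A reader might take 46 of 141 as a patient rate. It is not: states are counted equally, and the number of men entering by this route is not given. No count is offered for CD, where SAP Section 6.7 says only a few were enrolled. Men who entered as Week 13 Non-responders and whose scores stay level or fall are not affected.

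Nor does this bias the main result. The Week 13 primary analysis precedes open label, and the OL semen displays are descriptive. Amendment 6 states that the study is past its endpoint time points, so few or no men are likely to remain in this phase. It is a minor correction.

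**What to change.** In Section 3.4 and the Definition of Terms, state that in the Open-Label Filgotinib Phase (OL Day 1 through OL Week 13) Disease Worsening is measured from the OL Day 1 pMCS or CDAI, counting only visits after the first open-label dose. Add investigator-judged worsening as a further ground for stopping, as the LTE already has. This covers men who enter at pMCS 9, who cannot worsen further by score.

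The cost is wording only: both scores are already scheduled at OL Day 1, and no visit is added. The downside is that some men with persistently high scores would stay on open-label drug until OL Week 13 or until the investigator withdraws them.
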